2.1.3 Exploratory Objective

- To validate and assess FGFR family members (specifically, FGFR2 and potentially those harboring activating mutations) as predictive biomarkers.
- To evaluate the association between known markers of the FGF signaling pathway, toxicity, and clinical activity.

2.2 Overview of Study Design

2.2.1 Dose Schemes

This is an open-label phase 1/2 study of ARQ 087 in adult subjects with advanced solid tumors that has been enrolled in two parts. Part 1 enrolled subjects with solid tumors and Part 2 only enrolled subjects with FGFR genetic alterations, including intrahepatic cholangiocarcinoma with FGFR2 gene fusion. Treatment will be initiated at a dose level of 25 mg/QOD (every other day).

Part 1: Dose Escalation Cohorts

In cohorts 1-4, treatment consisted of two treatment periods: Treatment Period 1 (single dose administration for 72-hour PK assessment) and Treatment Period 2 (continuous dosing that will cease at the subject's discontinuation from the study).

Given the long half-life (about 1 week) of ARQ 087 in human subjects and the length of time (about 35 days) to reach steady state it was determined that it was reasonable to eliminate the single dose phase. Hence, starting with cohort 5, treatment consisted of a single treatment period of continuous dosing that ceased at the subject's discontinuation from the study.

The Maximum tolerated dose (MTD) was defined as the dose level at which no more than one subject with a DLT was observed among six subjects. Once the MTD was determined, up to six additional subjects might be treated at this dose level of ARQ 087. If the MTD was not reached, dose escalation would have to proceed with the purpose of determining a RP2D of ARQ 087.

Part 2: Expanded Cohort

Based on the drug safety profile and preliminary food-effect cohort PK data, 300 mg qd under fasting conditions has been defined as the RP2D and is recommended for further evaluation in the expanded cohort. Approximately 50-60 subjects with advanced solid tumors with FGFR genetic alterations, including iCCA with FGFR2 gene fusion planned to be enrolled in expanded cohort. The tumor type eligibility was to be confirmed by the Sponsor's Medical Monitor or designee prior to enrollment. If, at the time of the first restaging (C3D1), in two out of the first five enrolled subjects with the same tumor type, an objective response (significant, $\geq 15\%$, reduction in tumor size) was not achieved, such tumor sub-cohort would have to be closed for further enrollment.

There were 11 dose cohorts (Part 1 and Part 2) as listed below (see Table 1).

Table 1: Dosing Guidelines for ARQ 087

Part/Period	Cohort	Total Daily Dose ^a	Dose per Administration	Number of Subjects
Part 1/Period 1	1 ^a	25 mg	1 cap x 25 mg x qod	3-6 ^b
Part 1/Period 1	2	25 mg	1 cap x 25 mg x qd	3-6 ^b
Part 1/Period 1	3	50 mg	2 caps x 25 mg x qd	3-6 ^b
Part 1/Period 1	4	100 mg	1 caps x 100 mg x qd	3-6 ^b
Part 1/Period 2	5*	150 mg	2 caps x 25 mg & 1cap x 100 mg x qd	3-6 ^b
Part 1/Period 2	6	200 mg	2 caps x 100 mg x qd	3-6 ^b
Part 1/Period 2	7	250 mg	2 caps x 25 mg & 2 caps x 100 mg x qd	3-6 ^b
Part 1/Period 2	8	325 mg	1 cap x 25 mg & 3 caps x 100 mg x qd	3-6 ^b
Part 1/Period 2	9	425 mg	1 cap x 25 mg & 4 caps x 100 mg x qd	3-6 ^b
Part 1/Period 2	Food-effect ^a	400 mg	4 caps x 100 mg qd	at least 6
Part 2	Expanded ^c	300 mg	3 caps x 100 mg x qd under fasting conditions	approx. 50-60

* Starting from Cohort 5, the dose escalation followed a modified Fibonacci scheme (increase by 50%, 30%, and 25%). To avoid potential non-compliance due to capsule burden, the dose escalation was supposed to be stopped at the dose level of 550 mg/daily

^a Total daily dose must be administered one hour prior or two hours after the meal [Exceptions: 1) Cohort 1 is dosed every other day and 2) Food-effect Cohort]

^b If a DLT is seen in one of three treated subjects, an additional three subjects will be treated at the same dose level

^c Based on the safety profile and PK results of the Food-effect cohort, the dose of 300 mg qd under fasting conditions has been defined as MTD/RP2D and were further evaluated in the Expanded Cohort.

2.2.2 Schedule of Assessments

Safety, tolerability, pharmacokinetics (PK) and pharmacodynamics (PD) of ARQ 087 were assessed for the duration of the study.

Detailed assessment plans are listed in table 2 (Part 1: Cohort 1-4), table 3 (Part 1: Cohorts 5-10 and Food-effect Cohort) and table 4 (Part 2: Expanded Cohort).

Table 2: Schedule of Assessments (Part 1: Cohorts 1-4)

Tests & Procedures	Pre-Study Visit(s)	Treatment Period 1: Single-dose (PK) ¹		Treatment Period 2: Continuous Dosing Weekly Visits ¹						End of Treatment Visit	30-day Safety Follow-up
	Baseline			Cycle 1				Cycle 2+			
Week		0	0	1	2	3	4	1	3	7 days after the last dose of ARQ 087	30 days after the last dose of ARQ 087
Day	0	Day 1	Day 2, 3, 4	1	8	15	22	1	15		
Window	-21 – 0	0	0	0	± 3 days			± 3 days		+3 days	+3 days
Written Informed Consent	X										
Medical History	X										
Physical Examination ²	X	X		X	X	X	X	X	X	X	
ECOG PS	X	X		X	X	X	X	X	X	X	
Vital Signs, Weight ³	X	X	X	X	X	X	X	X	X	X	
Hematology ⁴	X	X		X	X	X	X	X	X	X	
Blood Chemistry ⁴	X	X		X	X	X	X	X	X	X	
Liver Function Tests ⁴	X	X		X	X	X	X	X	X	X	
Coagulation tests ⁴	X									X	
Thyroid function tests ⁴	X									X	
Urinalysis ⁴	X			X		X		X		X	

Serum Pregnancy Test⁴	X									X	
Tumor Markers, if applicable	X			X				X		X	
12-Lead ECG⁵	X			X		X		X		X	
Echocardiography or MUGA, if applicable⁵	X							X		X	
Pharmacokinetics⁶		X	X		X	X	X				
Pharmacodynamics⁶		X	X		X	X	X	X		X	
Archival and/or Fresh Tumor Biopsy⁷	X	X		X							
FGFR mutation, if unknown, Expanded Cohort only⁷	X										
Tumor Measurement and Staging⁸	X ⁹							X		X	
Concomitant Medications	X	X	X	X	X	X	X	X	X	X	
Adverse Events Assessment		X	X	X	X	X	X	X	X	X	X
ARQ 087 Dispensation		X		X	X	X	X	X	X		

1. Washout period between Treatment Period 1 Day 1 and Treatment Period 2 Cycle 1 Day 1 should be at least 72 hrs
2. Physical examination, including mucous membrane and skin
3. Weight at Baseline visit, on Day 1 and Day 15 of Cycle 1, on Day 1 of each subsequent cycle, and End of Treatment visit.
4. Refer to Section 6.4 for description of laboratory assessments

5. Refer to Section 6.3 for detailed description of assessments (Echocardiography or MUGA should be performed at Baseline, C3D1, C5D1, etc., and End of Treatment)
6. Refer to Sections 6.5 and 6.6 for pharmacokinetic and pharmacodynamic blood samples collection schedules. Note: Because Cycle 1 Day 22 and Day 23 visits are days when the full PK is performed, subjects enrolled in Cohort 1 (25 mg every other day) Cycle 1 Week 4 visits should be scheduled on the day of ARQ 087 administration and next consecutive day, when drug is not taken, e.g., Cycle 1 Day 21 and Day 22 or Cycle 1 Day 23 and Day 24.
7. Refer to Section 6.8 for detailed description of tumor tissue samples collection. If archival tissue is not available, baseline tumor biopsy will be performed to confirm FGFR mutation (the Expanded Cohort only).
8. Refer to Sections 6.7 and Appendix 6 for tumor evaluation description (Baseline, C3D1, C5D1, etc., and End of Treatment)
9. Unless tumor evaluation/measurement has been performed within 28 days prior to the first dose of ARQ 087

Table 3: Schedule of Assessments (Part 1: Cohorts 5-10 and Food-effect Cohort)

Tests & Procedures	Pre-Study Visit(s)	Continuous Dosing Weekly Visits								End of Treatment Visit	30-day Safety Follow-up
	Baseline	Cycle 1				Cycle 2+					
Week		1	2	3	4	1	3	7 days after the last dose of ARQ 087		30 days after the last dose of ARQ 087	
Day	0	1	2	8	15	22	23	1	15		
Window	-21 – 0	0		± 3 days				± 3 days		+3 days	±3 days
Written Informed Consent	X										
Medical History	X										
Physical Examination ¹	X	X		X	X	X		X	X	X	
ECOG PS	X	X		X	X	X		X	X	X	
Vital Signs, Weight ²	X	X	X	X	X	X	X	X	X	X	

Hematology³	X	X		X	X	X		X	X	X	
Blood Chemistry³	X	X		X	X	X		X	X	X	
Liver Function Tests³	X	X		X	X	X		X	X	X	
Coagulation tests³	X									X	
Thyroid function tests³	X									X	
Urinalysis³	X	X			X			X		X	
Serum Pregnancy Test³	X									X	
Tumor Markers, if applicable	X	X						X		X	
12-Lead ECG⁴	X	X			X			X		X	
Echocardiography or MUGA, if applicable⁴	X							X		X	
Pharmacokinetics⁵		X	X	X	X	X	X	X	X	X	
Pharmacodynamics⁵		X		X	X	X		X		X	
Archival and/or Fresh Tumor Biopsy⁶	X					X					
Tumor's genomic status, if unknown, Food-effect & Expanded Cohorts⁶	X										
Tumor Measurement and Staging⁷	X ⁸							X		X	
Concomitant Medications	X	X	X	X	X	X	X	X	X	X	
Adverse Events Assessment		X	X	X	X	X	X	X	X	X	X
ARQ 087 Dispensation		X		X	X	X		X	X		

1. Physical examination, including mucous membrane and skin

2. Weight at Baseline visit, on Day 1 and Day 15 of Cycle 1, on Day 1 of each subsequent cycle, and End of Treatment visit.
3. Refer to Section 6.4 for description of laboratory assessments
4. Refer to Section 6.3 for detailed description of assessments (Echocardiography or MUGA should be performed at Baseline, C3D1, C6D1, C9D1, etc., and End of Treatment)
5. Refer to Section 6.5 and 6.6 for pharmacokinetic and pharmacodynamic blood samples collection schedules.
6. Refer to Section 6.8 for detailed description of tumor tissue samples collection. If archival tissue is not available, baseline tumor biopsy should be performed. Paired biopsy is mandatory for subjects enrolled in the Expanded Cohort and Food-effect Cohorts.
7. Refer to Sections 6.7 and Appendix 6 for tumor evaluation description (Baseline, C3D1, C5D1, etc., and End of Treatment)
8. Unless tumor evaluation/measurement has been performed within 28 days prior to the first dose of ARQ 087

Table 4: Schedule of Assessments (Part 2: Expanded Cohort)

Tests & Procedures	Pre-Study Visit(s)	Continuous Dosing Weekly Visits						End of Treatment Visit	30-day Safety Follow-up
	Baseline	Cycle 1				Cycle 2+			
Week		1	2	3	4	1	3	7 days after the last dose of ARQ 087	30 days after the last dose of ARQ 087
Day	0	1	8	15	22	1	15		
Window	-21 – 0	0	± 3 days			± 3 days		+3 days	±3 days
Written Informed Consent	X								
Medical History	X								
Physical Examination ¹	X	X	X	X	X	X	X	X	
ECOG PS	X	X	X	X	X	X	X	X	

Vital Signs, Weight²	X	X	X	X	X	X	X	X	
Hematology³	X	X	X	X	X	X	X	X	
Blood Chemistry³	X	X	X	X	X	X	X	X	
Liver Function Tests³	X	X	X	X	X	X	X	X	
Coagulation tests³	X							X	
Urinalysis³	X	X		X		X		X	
Serum Pregnancy Test³	X							X	
Tumor Markers, if applicable	X	X				X		X	
12-Lead ECG⁴	X	X		X		X		X	
Echocardiography or MUGA, if applicable⁴	X					X		X	
Pharmacodynamics⁵		X	X	X	X	X		X	
Archival and/or Fresh Tumor Biopsy⁶	X				X				
Tumor's genomic status, if unknown, Food-effect & Expanded Cohorts⁶	X								
Tumor Measurement and Staging⁷	X ⁸					X		X	
Concomitant Medications	X	X	X	X	X	X	X	X	
Adverse Events Assessment		X	X	X	X	X	X	X	X
ARQ 087 Dispensation		X	X	X	X	X	X		

1. Physical examination, including mucous membrane and skin

2. Weight at Baseline visit, on Day 1 and Day 15 of Cycle 1, on Day 1 of each subsequent cycle, and End of Treatment visit.

3. Refer to Section 6.4 for description of laboratory assessments
4. Refer to Section 6.3 for detailed description of assessments (if applicable, Echocardiography or MUGA should be performed at Baseline and End of Treatment. If clinically indicated the test may be done at any time during the study treatment.)
5. Refer to Section 6.5 and 6.6 for pharmacokinetic and pharmacodynamic blood samples collection schedules.
6. Refer to Section 6.8 for detailed description of tumor tissue samples collection. If archival tissue is not available, baseline tumor biopsy should be performed. Paired biopsy is optional for subjects enrolled in the Expanded Cohort.
7. Refer to Sections 6.7 and Appendix 6 for tumor evaluation description (Baseline, C3D1, C5D1, etc., and End of Treatment)
8. Unless tumor evaluation/measurement has been performed within 28 days prior to the first dose of ARQ 087

3 DEFINITIONS AND DATA PROCESSING RULES

3.1 Definitions

3.1.1 Study Drug and Treatment Group

Study drug refers to ARQ 087.

11 cohorts with different dose and frequency are designed and used in this study, for analyses, cohorts will be grouped into four treatment groups as below:

- Low Dose Group (25 mg QOD – 200 mg QD)
- Middle Dose Group (250 mg QD – 325 mg QD)
- High Dose Group (400 mg QD – 425 mg QD)
- Expanded Cohort Group (300 mg QD)

3.1.2 Study Day

The study day for all safety and non-safety (e.g., tumor assessment, death, disease progression, tumor response, performance status) assessments is calculated as:

For days on or after start date of study drug:

Study day = the date of the event (visit date, onset date of an event, assessment date etc.) - start date of study drug + 1.

The first day of study drug is therefore study Day 1. Example: If the start of study drug is on 01JAN2013 and start date of an adverse event is on 05JAN2013, then the study day of the adverse event onset is 5.

For days prior to start date of study drug the study day is negative:

Study Day = event date - start date of study drug.

The study day will be derived in the SDTM data sets.

3.2 Analysis Variables

3.2.1 Demographic and Baseline Variables

Demographics and baseline characteristics will include but not limit to:

- Demographics
- Baseline disease characteristics

- Clinically significant medical history, including surgeries
- Prior therapies
- Concomitant medications and treatments

3.2.2 Safety Variables

Safety variables include adverse events, laboratory test, vital signs, ECOG PS, ECG and physical examination.

3.2.3 Pharmacokinetics and Pharmacodynamic Variables

PK parameters include C_{max} , AUC and half-life.

PD parameters include phosphate, glucose, FGF, 19, 21, and/or 23 from blood sample.

3.2.4 Efficacy Variables

Best Overall Response (BOR)

The best overall response is determined once all the data for the subject is known. No confirmatory measurement for CR or PR is required in this study. The best overall response is defined as the best response (in the order of CR, PR, SD, and PD) among all overall responses recorded from the start of treatment until the last radiographic tumor assessment (for example, a subject who has SD at first assessment, PR at second assessment, and PD on last assessment has a best overall response of PR). When SD is believed to be the best response, it must also meet the protocol specified minimum time from baseline, 8 weeks (± 3). If the minimum time is not met when SD is otherwise the best time point response, the subject's best response depends on the subsequent assessments. For example, a subject who has SD at first assessment, PD at second and not meeting minimum duration of SD will have a best response of PD. The same subject lost to follow-up after the first assessment would be considered non-evaluable.

Objective Response Rate (ORR)

For purposes of determining the objective response rate (ORR), tumor response will be based on the best overall response recorded for each subject from the date of first dose. The ORR will be calculated as the number of subjects with a complete or partial response divided by the total number of subjects [ORR= (CR+PR)/# subjects].

Disease Control Rate (DCR)

Disease Control Rate (DCR) is defined as the proportion of subjects with the best overall responses of CR, PR and SD [DCR= (CR+PR+SD)/# subjects].

Duration of Objective Response

Duration of objective response is defined as the time from the date of the measurement criteria are first met for CR/PR (whichever is first recorded) until the first date that recurrent or progressive disease is documented.

If a subject is discontinued, dies, or is lost to follow-up with no documentation of progressive disease, duration of response is defined as the time from the date of the first documentation of objective response to the date of the last tumor assessment as a censored value. Duration of response will be measured for responding subjects (PR or CR) only.

Duration of Stable Disease

Duration of stable disease is defined as the time from the start of the treatment until the criteria for disease progression are met.

If a subject is discontinued or dies, or is lost to follow-up with no documentation of progressive disease, duration of stable disease is defined as the time from the date of first dose to the date of the last tumor assessment as a censored value. Duration of stable disease is measured for any subject who has best overall response of SD.

Progression-Free Survival (PFS)

Progression Free Survival (PFS) is defined as time from first dose until documented radiographic disease progression or death, whichever occurs first.

If a subject is discontinued from study due to reasons other than radiographic disease progression or death, PFS is censored as the time from the date of first dose to the date of the last tumor assessment. Only assessments with CR, PR SD or NE as overall tumor response are treated as last tumor assessment.

If a subject has no baseline tumor assessment and/or has no post baseline tumor assessment, this subject is to be censored at the date of first dose for PFS.

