## 6.7 Tumor Evaluation

Tumor assessments (CT scan, PET scan, or MRI) will be performed at Baseline, and every eight weeks (e.g., on Day 1 of every odd cycle, Day 1 Cycle 3, Day 1 Cycle 5, or Week 8, Week 16, etc.) or as otherwise clinically indicated.

For subjects who do not experience disease progression and continue to benefit from the treatment after 11 cycles, tumor evaluation may be performed every 3 months (e.g., Day 1 of Cycle 14, Day 1 of Cycle 17, Day 1 of Cycle 20, etc.) upon agreement between the Investigator and ArQule's Medical Monitor.

Standard imaging studies should be performed according to institutional procedures and/or standard of care. Tumor response will be evaluated using relevant guidelines (see Appendix 6 for RECIST 1.1 guidelines).

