#### **Evaluation of Target Lesions**

- *Complete Response (CR)*: Disappearance of all target lesions. Any pathological lymph nodes (whether target or non-target) must have reduction in short axis to < 10 mm.
- *Partial Response (PR)*: At least a 30% decrease in the sum of diameters of target lesions, taking as reference the baseline sum diameters.
- *Progressive Disease (PD)*: At least a 20% increase in the sum of diameters of target lesions, taking as reference the smallest sum on study (this includes the baseline sum if that is the smallest on study). In addition to the relative increase of 20%, the sum must also demonstrate an absolute increase of at least 5 mm. (Note: the appearance of one or more new lesions is also considered progression).
- *Stable Disease (SD)*: Neither sufficient shrinkage to qualify for PR nor sufficient increase to qualify for PD, taking as reference the smallest sum diameters while on study. In this study, the minimum duration for SD is defined as 8 weeks ( $\pm$  2 days).

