### Frequency of Tumor Re-evaluation

In this study, tumor measurement will be conducted at Baseline, and then in 8-week intervals while the subject is on treatment or as clinically indicated until progression of disease,

withdrawal of consent, death, or loss to follow-up. Tumor measurement will also be performed during the End-of-Treatment visit if it is not done within 28 days of the visit date.

Baseline tumor assessments must be performed within four weeks (28 days) of the first dose of treatment.

All efforts should be made to ensure consistency between the baseline measurements and all subsequent measurements in reference to utilization of scanning methods, equipment, technique (including slice thickness and field of view), and the radiographic interpreter.

The radiological evaluation must include CT or MRI scanning of the chest, abdomen, and pelvis. Any additional suspected sites of disease should also be imaged. All evaluations should meet the standard of care for imaging of lesions in the respective organ(s).

All target and non-target sites are evaluated at each time point of tumor assessment.

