### **Confirmatory Measurement/Duration of Response**

#### Confirmation

Confirmation of PR and CR is NOT required in this study.

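### ORR rests on the best of all scans with no confirmation, so measurement error can push it upward; a confirmed ORR should be added beside it as a sensitivity analysis

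*SAP*

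**What the plan says.** SAP 3.2.4 takes best overall response as the best value "among all overall responses recorded from the start of treatment until the last radiographic tumor assessment". It adds "No confirmatory measurement for CR or PR is required in this study", and its own worked example counts SD, then PR, then PD as a PR. ORR follows directly: "tumor response will be based on the best overall response recorded for each subject from the date of first dose". Protocol Appendix 6 agrees, under Evaluation of Best Overall Response and again under Confirmation: "Confirmation of PR and CR is NOT required in this study".

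For target lesions, PR is "At least a 30% decrease in the sum of diameters of target lesions, taking as reference the baseline sum diameters". On timing, Appendix 6 says "tumor measurement will be conducted at Baseline, and then in 8-week intervals while the subject is on treatment", and Protocol 6.7 gives the same interval. After 11 cycles, "tumor evaluation may be performed every 3 months".

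SAP 5.4.5 tabulates ORR with a 95% CI in the safety and evaluable populations. It also lists the percent change in the target-lesion sum and plans a waterfall plot. Neither document plans a confirmed ORR or describes an independent read. The study is open-label (Protocol 7.5), and every subject receives ARQ 087.

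**The concern.** A best-of-all rule without confirmation moves a subject in one direction only. One low reading creates a PR, and no later reading takes it away. Each further scan is another chance for random error to cross the 30% line. No control arm shares the bias, and the planned 95% CI does not cover it.

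The protocol recognises the mechanism. In Appendix 6, the 5 mm default for lesions too small to measure is there to prevent false responses caused by measurement error. The same appendix uses the next scheduled scan to settle equivocal progression, but plans nothing similar for response.

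At stake is how far the ORR can be relied on as preliminary evidence of activity and as a guide to the target population, both of which are secondary objectives (Protocol 2.2).

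**Working it through.** **No plan figure to reproduce.** The documents give no null ORR, target ORR, power or alpha for response (SAP 5.1; Protocol 10).

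**Inputs from the documents.** The PR cut-off is a 30% decrease from the baseline sum. Scans are 8-weekly. Most subjects are expected to be treated for 4 to 24 weeks (Protocol 4.6). That gives from no scheduled scan (4 < 8) up to 24/8 = 3.

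**Assumptions, not in the documents.** The error SD *s* of the log sum of diameters is 5%, 8% or 10%, independent at baseline and at each scan. True change *c* is constant over the scans. New lesions, non-target lesions and dropout are ignored.

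**Step 1: one scan.** Observed change = (1 + c)·exp(scan error − baseline error) − 1, so

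P(called PR) = Φ( ln[0.70/(1 + c)] / (s√2) ).

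For c = −20%, ln(0.70/0.80) = −0.1335. Dividing by 0.0707, 0.1131 and 0.1414 gives z = −1.89, −1.18 and −0.94, so P = 2.9%, 11.9% and 17.3%.

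**Step 2: three scans.** By simulation. Unconfirmed means any scan meets PR; confirmed means two consecutive scans do. Entries are for s = 5% / 8% / 10%.

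| True change | Called PR, unconfirmed | Called PR, confirmed |
|---|---|---|
| 0% | at most 2% | about 0% |
| −20% | 7% / 25% / 34% | 1% / 6% / 10% |
| −26% | 41% / 55% / 59% | 14% / 22% / 26% |

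The effect comes from shrinkage close to 30%, not from subjects with no shrinkage. Confirmation does not remove it fully, because every scan is compared with the same baseline sum and shares its error.

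**Step 3: a population.** Assume true change has mean −15% and SD 20 points. True ORR = Φ((−0.30 + 0.15)/0.20) = Φ(−0.75) = 22.7%.

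| Scans per subject | Unconfirmed ORR | Confirmed ORR |
|---|---|---|
| 1 | 24% / 25% / 26% | 0% by construction |
| 2 | 27% / 30% / 32% | about 20% |
| 3 | 28% / 32% / 35% | 22% / 22% / 23% |

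The excess of the unconfirmed ORR runs from 24 − 22.7 = 1.3 points (one scan, s = 5%) to 35 − 22.7 = 12.3 points (three scans, s = 10%).

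**Step 4: what confirmation loses.** With three scans in this population, the confirmed rule misses 13% / 19% / 22% of true responders; the unconfirmed rule misses 4% / 6% / 7%. A subject with a true 34% shrinkage is confirmed in 76% / 64% / 60% of cases.

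**The case against.** The strongest case for the plan as written is that non-confirmation is deliberate, pre-specified and the same in both documents. The primary objective is safety, anti-tumor activity is exploratory, and no hypothesis is tested. Protocol 10.2.3 names response rate, disease control rate and PFS together, so ORR is not the sole activity measure. The target-lesion listings and waterfall plot already let a reader find near-threshold responses. All of this stands: the addition improves reporting and corrects no error.

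The sizes also depend on an assumed error SD, and three scans is the top of the range expected for most subjects. That stands too, so the one-scan and two-scan rows belong beside the three-scan row.

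A confirmed ORR has its own bias. With an equal mix of one, two and three scans, independent of response (a further assumption), unconfirmed ORR is 26% / 29% / 31% and confirmed ORR is 14% / 14% / 14%, against a true 22.7%. Responders probably stay on treatment longer, which would soften this. The point still holds, and it is why the confirmed figure should not replace the planned one.

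Three stronger readings are tempting, but the documents do not support them:

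- **That the iCCA subject with a 26% maximum reduction (Protocol 4.1.1) shows the error.** That subject's status is given as SD, which agrees with the 30% cut-off. The loose sentence before it, which counts both subjects as objective responses, has nothing to do with confirmation.
- **That the iCCA futility look is invalidated.** No null rate, target rate or error rates are stated for it, so there is no stated property for this bias to breach.
- **That a confirmed ORR is free.** It is free in imaging only. Scanning is tied to treatment, the end-of-treatment scan is omitted if one was done within 28 days (Protocol 5.6), and the interval may lengthen after 11 cycles. Some responses therefore cannot be confirmed.

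**Conclusion.** The point holds as a limitation with an inexpensive remedy. The unconfirmed best-of-all rule biases ORR upward; the direction follows from the definition, and the size does not. Under the assumptions above the excess is about 1 to 12 points on a true ORR of 22.7%, growing with the error SD and the number of scans, and arising mainly from true shrinkage near 30%. A confirmed ORR is close to the true value only when subjects have about three scans, and falls below it with fewer. Neither figure is sufficient alone; shown together, they indicate how much of the ORR rests on a single scan.

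**What to change.** Keep the unconfirmed best overall response and ORR as planned, and leave the timing of the iCCA futility look unchanged. Requiring confirmation there would delay it by about one 8-week interval.

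Before database lock, add to SAP 3.2.4 and 5.4.5, labelled as a sensitivity analysis:

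1. A confirmed ORR (CR or PR criteria met again at the next evaluable scheduled assessment) with a 95% CI. Show it beside the unconfirmed ORR, on the same denominators, for the Expanded Cohort and for FGFR2-fusion iCCA.
2. A rule that a response on the last available scan counts as unconfirmed, with the number of such subjects reported.
3. A rule for a missing or NE next scan. One option is to use the following evaluable scheduled scan if progression has not intervened, and otherwise to count the response as unconfirmed. Say also whether the end-of-treatment scan can confirm.
4. A note that the two figures are to be read together, because the unconfirmed ORR tends to overstate and the confirmed ORR can understate.

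The cost is one derived variable, one table row and a lower second figure. SAP 5.4.5 tabulates by dose group, so FGFR2-fusion iCCA needs its own column for both figures. No extra scans are needed.
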